7.3. Tertiary endpoint Analyses

Tertiary endpoints included in the analysis are individual components of the primary composite outcome of all-cause mortality, MI, coronary revascularization, acute renal failure, or post-randomization stroke at 90 days. All are considered as binary variables in the study, and the effect of transfusion strategy on these endpoints will be analyzed initially with a Pearson chi-square test (Tables 22a-e). The test for differences between transfusion strategies in each tertiary outcome will be conducted at an α -level of 0.01. Additional analyses will be carried out by taking account of age, RCRI, and nadir Hb using logistic regressions (Tables 23a-e), as stated in the secondary endpoint analyses. The analyses will be done in the ITT, mITT, No-Recent-Transfusion, Completers, and Per Protocol populations.

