no events. We stratified the patients as being high risk for cardiac events if they had history of IHD, peripheral artery disease (PAD), or underwent a PAD-related operation. We ultimately collected information on 171,357 patients who underwent the target operations and were included in our analysis.

FIGURE 2. Probability of the Composite Endpoint at Various Levels of the Postoperative Nadir Hb – Multicenter data

Similarly to the single institutional analysis, a strong association was seen between increasing values of nadir postoperative Hb and freedom from the composite endpoint (OR: 0.566, 95% CI: 0.561 to 0.57, Figure 2). From the initial patient pool, 38,153 patients were at high risk for cardiac events and dropped their nadir postoperative Hemoglobin in the early postoperative period below 10 gm/dl, conditions that would make them eligible for the proposed trial. In this high cardiac risk patient population, the composite outcome occurred in almost 30% of patients with nadir Hb between 6-9 gm/dl (a subset that will represent the restrictive transfusion arm in the proposed study) and in 15% of patients with nadir Hb between 9-10 gm/dl (a subset that will represent the liberal transfusion arm in the proposed trial). Event rates for the composite and individual endpoints are summarized in TABLE 2 below:

TABLE 2. Composite Event Rates and Individual Event Rates among Veterans at High Cardiac Risks after a Surgical Procedure

Nadir Hb	Composite Endpoint	Death	MI	ARF	Coronary Revascularization
6-9 gm/dl	29.5%	15.3%	11.0 %	11.1%	0.4%
9-10 gm/dl	15.0%	6.9%	6.2%	4.1%	0.3%

III. SIGNIFICANCE AND RELEVANCE TO VETERANS

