4.5. Sample Size Consideration

The sample size estimation and power analysis are based on the hypothesis testing of the primary composite endpoint of all-cause post-randomization mortality, myocardial infarction (MI), coronary revascularization, acute renal failure, or post-randomization stroke up to 90 days after randomization. The primary hypothesis of the study is that in VA patients with high cardiac risk undergoing a surgical procedure, a significantly smaller proportion of participants receiving blood under a liberal transfusion strategy will experience the composite endpoint compared to participants under restrictive transfusion strategy at 90 days after randomization. The primary analysis will be done as an "intent-to-treat" analysis. Our database review revealed that 29.8% out of 25,343 patients in the VA population who were at high cardiac risk and had nadir postoperative Hb range between 6-9 gm/dl developed the composite endpoint of death, MI, acute renal failure, or coronary revascularization within 90 days from the index operation. Based on the analysis, a baseline event rate of 30% for the composite endpoint is expected in the restrictive group. We also assume a 25% reduction or 22.5% event rate in the liberal group. To detect the expected 7.5 percentage point difference or 25% reduction, a sample size of 1444 will be required at 90% power, 5% type-I error rate and with a two-sided test (Appendix 3). Assuming 5% dropout rate, then 1520 participants (or 760/group) will be needed to achieve the desired testing power.

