7. EFFICACY ANALYSES

The primary analysis of the study will be performed on the primary endpoint on the ITT population. The secondary analyses will be performed on the secondary and tertiary endpoints on the ITT population, as well as the analyses performed on all the primary, secondary, and tertiary endpoints on the mITT, No-Recent-Transfusion, Completers, and Per Protocol populations unless otherwise specified. Potential difficulties of convergence of model fit, which may arise in efficacy analyses that include covariates, will be handled using the method described in Section 7.1.

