variable. We will also consider the Akaike Information Criterion statistic and the Schwartz Criterion statistic, both of which adjust the -2 log likelihood for the number of items in the model. Models that show lack of fit will be reconsidered for the inclusion of additional variables or use of alternate models with assumptions that are better met by the study data. One alternate model if the model fit is poor for logistic regression is a log-linear model. For logistic regression analysis, if the coefficient for intervention effect is significant (i.e., the confidence interval for the odds ratio does not include 1), then the null hypothesis of no intervention effect adjusting for other covariates in the final model will be rejected. The P value for testing each covariate coefficient in the model being zero will be based on Wald test (Table 17a-e). The primary analysis will be done in the ITT population. Additional analyses will be done in the mITT, No-Recent-Transfusion, Completers, and Per Protocol populations.

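### SAP Section 7 relies on a convergence method that Section 7.1 does not contain, and the adjusted model for coronary revascularization (about 5 expected events) is likely to need one

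*SAP*

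**What the plan says.** SAP 7.3 first compares each of the five components by a Pearson chi-square test at the 0.01 level. It then adds an adjusted model: "Additional analyses will be carried out by taking account of age, RCRI, and nadir Hb using logistic regressions". The Table 23 shell lists treatment, age, RCRI classes 1 to 4 and nadir Hb for every component, with an odds ratio and a 99% interval. The table is repeated in five analysis populations.

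The introduction to SAP Section 7 recognises that covariate models may fail to converge and says such difficulties "will be handled using the method described in Section 7.1". Section 7.1 covers linearity in the logit, the -2 log likelihood, and the Akaike and Schwartz criteria. For lack of fit it allows further variables or another model, with a log-linear model as the example. On inference it says: "The P value for testing each covariate coefficient in the model being zero will be based on Wald test". It does not mention convergence, separation, sparse data, or penalised or exact estimation.

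**The concern.** The SAP foresees the problem and points to a remedy that is not there. The fallback that 7.1 does give would not help. Adding variables makes sparsity worse, and a log-linear model fitted by maximum likelihood has the same unbounded estimates when a cell is empty.

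This would be only an editorial matter if every model had plenty of events. Coronary revascularization does not. With so few events, an arm or an RCRI class can easily have none. The corresponding maximum-likelihood coefficient then has no finite value, and its Wald p-value and interval carry no information. Without a written rule, the analyst must decide after seeing the data whether to drop covariates, merge RCRI classes, penalise the likelihood or leave the row blank. Readers use component results to interpret a composite, so that choice is better made in advance.

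**Working it through.** **Inputs.** 760 per group and 1520 in total (SAP 4.5). Coronary revascularization 0.4% at nadir Hb 6–9 gm/dl and 0.3% at 9–10 gm/dl (protocol Section II, Table 2), which the protocol treats as stand-ins for the restrictive and liberal arms. Stroke about 1% (protocol Section II c, single-institution vascular data), assumed equal in both arms. The documents give no RCRI distribution, so several mixes are assumed, with equal risk across classes.

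**The plan's own figure.** n per arm = [1.960·√(2·0.2625·0.7375) + 1.2816·√(0.30·0.70 + 0.225·0.775)]² / 0.075² = 721.2, rounded up to 722, so 1444 in total. Then 1444/0.95 = 1520. The stated sample size reproduces.

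**Expected events.**
- Revascularization: 760 × 0.004 + 760 × 0.003 = 3.04 + 2.28 = 5.3 (Poisson 95% range 1 to 10). With 722 per arm it is 5.1.
- Stroke: 2 × 760 × 0.01 = 15.2.
- Death: 760 × (0.153 + 0.069) = 169. MI: 760 × (0.110 + 0.062) = 131. Renal failure: 760 × (0.111 + 0.041) = 116.

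**Events per parameter.** Treatment 1, age 1, RCRI 3 contrasts and nadir Hb 1 make 6. Revascularization: 5.3/6 = 0.9, or 5.3/4 = 1.3 if RCRI were entered as a linear term. Stroke: 15.2/6 = 2.5.

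**Empty arm.** P = e^(-3.04) + e^(-2.28) − e^(-5.32) = 0.048 + 0.102 − 0.005 = 14.5%. For stroke, 2·e^(-7.6) − e^(-15.2) = 0.1%.

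**Empty arm or RCRI class.**

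| Assumed RCRI mix, classes 1–4 | Revascularization | Stroke |
|---|---|---|
| 25/25/25/25 | 72% | 9% |
| 15/40/30/15 | 79% | 20% |
| 10/40/30/20 | 82% | 27% |
| 5/50/30/15 | 91% | 53% |

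Maximum-likelihood fits of the six-parameter revascularization model failed or gave unbounded standard errors in 73% (first mix) and 82% (third mix) of 1000 simulated trials.

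**Which coefficient diverges.** In 300 simulated trials with the 15/40/30/15 mix, a linear-programming check found that the treatment coefficient diverged in 12%. These were exactly the trials with an empty arm, although about 80% had some empty cell. An empty RCRI class sends only that class's coefficient to infinity.

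**Precision when the estimate is finite.** Take 2 liberal and 3 restrictive events, unadjusted. The odds ratio is (2/758)/(3/757) = 0.67, the standard error of its log is √(1/2 + 1/758 + 1/3 + 1/757) = 0.91, and the 99% interval is 0.06 to 7.0.

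**Unadjusted test.** The expected count per arm is 2 to 3, below the usual 5. A 5–0 split gives Pearson p = 0.025 and Fisher p = 0.062, so five events cannot reach 0.01. Exact enumeration at a common rate of 0.35% gives a Pearson size of 0.28% at the nominal 1%, so the test is conservative.

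**The case against.** The strongest reply is that little depends on this. These are additional adjusted models for tertiary outcomes, they follow an unadjusted test that does not inflate type I error here, and the primary analysis does not use them. That is right, and it limits the point to minor importance.

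Several stronger readings are tempting but not supported:

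- **That about three-quarters of trials would give a meaningless treatment effect.** The 72–82% counts any empty arm or RCRI class. The treatment odds ratio is lost only when an arm is empty, in about 14–15%. Otherwise it is finite and very imprecise.
- **That rare components in general are affected.** Only revascularization has about 5 events. Stroke has about 15 and almost never an empty arm, and the other three exceed 100.
- **That site and interaction terms make it worse.** They appear in protocol Section XVI.E and its Table 4. SAP 7.3 and the revascularization and stroke blocks of Table 23 do not list them, and protocol Section XVI.H lets the SAP record departures from the protocol's plan.
- **That Wald tests are stated for Table 23.** They are stated for Table 17. They reach 7.3 through its reference to 7.2 and from there to 7.1.
- **That 7.1 has no fallback at all.** Its lack-of-fit provision may be what Section 7 meant. Even so, it gives no remedy for separation.

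It is also fair that Table 2 is retrospective, grouped by nadir Hb and counted from the operation, whereas the trial counts from randomization and also collects non-VA hospital records. Five events is therefore a planning estimate.

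**Conclusion.** The concern holds in a limited form. The missing convergence method can be confirmed from the text alone and affects every covariate-adjusted efficacy model that relies on the introduction to Section 7. Its practical effect is concentrated in one component. For coronary revascularization, at the Table 2 rates and full enrolment, the treatment odds ratio would be 0 or infinite in about one trial in seven. At least one coefficient would diverge in roughly 72–82% of trials under three of the RCRI mixes tried, and in 91% under the most skewed. The first figure rests on the Table 2 rates; the others rest also on the assumed RCRI mix and equal risk across classes. The four subset populations can only have the same number of events or fewer. The primary endpoint analysis and the sample size are unaffected.

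**What to change.** Add to SAP 7.1 the rule that Section 7 already says is there. When separation or non-convergence occurs, or when a component is too sparse for the planned model (naming at least coronary revascularization), fit the adjusted model by Firth penalised logistic regression, with profile-likelihood intervals and p-values in place of maximum likelihood with Wald. State in Table 22 that an exact or mid-P test replaces Pearson when an expected cell count is below 5. The numerical definition of too sparse, and whether to reduce the covariates for such components, are for the sponsor to choose. Keeping only treatment and four-class RCRI would retain the factor behind most empty cells.

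The cost is a few sentences of SAP text, the FIRTH option in PROC LOGISTIC (a procedure 7.1 already allows), a little extra programming, and slight shrinkage of the odds ratios. Sample size, data collection and the primary test do not change.

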7.4. Other Analyses

Age of blood in relation to 90-day composite endpoint, wound infection, and pneumonia

Analyses will be conducted of the associations between characteristics of transfused blood and three outcome measures: 90-day composite endpoint (Tables 24a-e), wound infection (Tables 25a-e), and pneumonia (Tables 26a-e). Current data collection plans call for blood expiration dates and the age of each unit of blood transfused will be calculated. Logistic regression models will be fitted to test for association between these outcomes and age of blood transfused (entered in different models as oldest unit transfused or as mean age of all units transfused). The analyses will be adjusted for baseline age, RCRI, nadir Hb, and the transfusion intervention. The test for differences of these outcomes will be conducted at an α -level of 0.05 for the primary outcome and 0.01 for wound infection and pneumonia. The analyses will be done in the ITT, mITT, No-Recent-Transfusion, Completers, and Per Protocol populations.

Time-to-event analysis for primary and major secondary endpoints

Survival analysis techniques will be used to analyze the time-to-event data for the primary and major secondary endpoints. Kaplan-Meier method will be used to estimate the survival (not experiencing event) over time in the two intervention groups and a log-rank test

will be used to compare the survival functions in the two groups for the primary endpoint and the secondary endpoints using PROC LIFETEST. Cox's Proportional Hazards models will be used to test the effect of the intervention on the time until endpoint events adjusted for age, RCRI, and nadir Hb, as described in the primary endpoint (Tables 27a-e, with an α -level of 0.05), and secondary endpoint (Tables 28a-e, with an α -level of 0.01) analyses using PROC PHREG. The analyses will be done in the ITT, mITT, No-Recent-Transfusion, Completers, and Per Protocol populations.

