a) The study proponent has performed a propensity score matched analysis of participants undergoing elective open surgical intervention for PAD.²⁸ The primary objective of this study was to assess the independent effects of nadir postoperative Hb (nHb) level and transfusion on a composite outcome of death or acute coronary syndrome (ACS) up to 30 days postoperatively. Secondary endpoints included perioperative wound and respiratory complications; and death or adverse cardiac events during an average follow-up of 24 months. A total of 1074 PAD-related operations were examined. In light of reports indicating a harmful effect of blood transfusion on mortality and cardiac outcomes, the analysis was adjusted for units of PRBCs transfused prior to the occurrence of any of the events that consisted of components of the composite outcome. Level of statistical significance in this study was set at alpha 0.0125 to account for the four comparisons performed when assessing the primary endpoint (two exposures tested against two individual outcomes).

TABLE 1: Effect of Nadir Hb and Units of Blood Transfused on a Composite Endpoint of Death, or ACS

Variable	Odds Ratio	Standard Error	P-Value	95% Confidence Interval
Nadir Hb < 10gm/dl	Reference	Reference	Reference	Reference
Nadir Hb ≥ 10gm/dl	0.62	0.17	0.120	0.33-1.14
Transfusion units	1.11	0.05	0.025	1.01-1.22

Univariate analysis in this study demonstrated a relative protective but not statistically significant effect of nHb ≥ 10 gm/dl on the composite endpoint of death or ACS (OR: 0.68, 95% CI: 0.54 to 1.19, p=0.12). On the multivariable model that included as predictors both nHb and units of blood transfused, nHb ≥ 10 gm/dl was again seen to have a relative protective effect on the composite endpoint, although again this difference did not reach statistical significance. (OR:

Transfusion Trigger after Operations in High Cardiac Risk Patients (TOP)

[figure not shown]
5

Version Number: 11 Date: 12/18/2024

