The active follow up period for study purposes will be up to 90 days after randomization. If the participant refuses to continue participation during active follow up, his or her participation in the study will be terminated. All participants who complete the active follow-up phase of the study will be followed up to one year by the Chair's Office to assess mortality using a combination of phone call follow-up, search of the DAF, or electronic medical record

assessment. If a participant declines to participate in long term follow up then one year mortality data for this participant will not be collected. Given that the one year follow up is passive and does not involve any participant action we do not anticipate this to become a major issue.

X. TRANSFUSION STRATEGIES

Participants will be randomized to a liberal (transfuse if Hb <10 gm/dl) or restrictive (transfuse if Hb <7gm/dl) transfusion groups. Transfusion will be administered in order to maintain Hb just above the aforementioned thresholds for the index hospital stay or up to 30 days after randomization, whatever comes first. A participant must be randomized within 24-hrs of the first postoperative Hb falling below 10 gm/dl. It is strongly recommended that the transfusion treatment is initiated as soon as possible after and no longer than 24 hours from identifying a protocol-required transfusion Hb threshold. Transfusions will be administered according to the following scheme.

- A. Liberal group (transfusion trigger: Hb < 10 gm/dl)
 - i. If Hb < 7.5 gm/dl transfuse three units PRBCs, then check Hb. Based on the return Hb value, follow the transfusion protocol (steps i, ii, or iii) until Hb \geq 10.
 - ii. If $7.5 \leq$ Hb < 8.5 gm/dl transfuse two units PRBCs, then check Hb. Based on the return Hb value, follow the transfusion protocol (steps i, ii, or iii) until Hb \geq 10.
 - iii. If Hb \geq 8.5 gm/dl transfuse one unit PRBCs, then check Hb. Based on the return Hb value, follow the transfusion protocol (steps i, ii, or iii) until Hb \geq 10.
- B. Restrictive group (transfusion trigger: Hb < 7 gm/dl)
 - i. If Hb < 5.5 gm/dl transfuse of two units PRBCs, then check Hb. Based on the return Hb value, follow the transfusion protocol (steps i, or ii) until Hb \geq 7.
 - ii. If $5.5 \leq$ Hb < 7 gm/dl transfuse one unit PRBCs, then check Hb. Based on the return Hb value, follow the transfusion protocol (steps i, or ii) until Hb \geq 7.

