Outcomes		Liberal	Restrictive	All Subjects	χ^2	p-Value
		(N =)	(N =)	(N=)		
90-day all-cause mortality	Present					
	Absent					
	Total					
90-day MI	Present					
	Absent					
	Total					
90-day coronary revascularization	Present					
	Absent					
	Total					
90-day stroke	Present					
	Absent					
	Total					
90-day acute renal failure	Present					
	Absent					
	Total					

Table 23a-e. Transfusion Related Individual Components of the Composite Endpoint, Logistic Regression (ITT, mITT, No-Recent-Transfusion, Completers, Per-Protocol)

	Outcomes	Coefficients	SE	p-Value	OR	OR 99% C.I.	
						Lower	Upper
90-day all-cause mortality	Liberal vs Restrictive						
	Age						
	RCRI						
	1						
	2						
	3						
	4						
	Nadir Hb						
	Transfusion and Age						
	Liberal vs Restrictive						
90-day MI	Age						
	RCRI						
	1						
	2						
	3						
	4						
	Nadir Hb						
	Liberal vs Restrictive						
	Age						
	RCRI						
90-day coronary revascularization	1						
	2						
	3						
	4						
	Nadir Hb						
	Liberal vs Restrictive						
	Age						
	RCRI						
	1						
	2						
90-day stroke	3						
	4						
	Nadir Hb						
	Liberal vs Restrictive						
	Age						
	RCRI						
	1						
	2						
	3						
	4						

	Outcomes	Coefficients	SE	p-Value	OR	OR 99% C.I.	
						Lower	Upper
90-day acute renal failure	Liberal vs Restrictive						
	Age						
	RCRI						
	1						
	2						
	3						
4							
	Nadir Hb						

Tables 24a-e. Effect of Age of Blood Transfused on Primary Outcome (ITT, mITT, No-Recent-Transfusion, Completers, Per-Protocol)

Factors	Coefficients	p-Values (Wald test)	OR (95% C.I.)
Using oldest unit transfused			
Age of Blood Transfused			
Liberal vs Restrictive			
Baseline Age of Participant			
RCRI			
1			
2			
3			
4			
Nadir Hb			
Using mean age of all the units transfused			
Age of Blood Transfused			
Liberal vs Restrictive			
Baseline Age of Participant			
RCRI			
1			
2			

3			
4			
Nadir Hb			

Tables 25a-e. Effect of Age of Blood Transfused on 90-day Wound Infection (ITT, mITT, No-Recent-Transfusion, Completers, Per-Protocol)

Factors	Coefficients	p-Values (Wald test)	OR (99% C.I.)
Using oldest unit transfused			
Age of Blood Transfused			
Liberal vs Restrictive			
Baseline Age of Participant			
RCRI			
1			
2			
3			
4			
Nadir Hb			
Using mean age of all the units transfused			
Age of Blood Transfused			
Liberal vs Restrictive			
Baseline Age of Participant			
RCRI			
1			
2			
3			
4			
Nadir Hb			

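### The age-of-blood models can use only participants with at least one unit, count units given after the outcome, and print a Liberal vs Restrictive odds ratio that is not a randomized comparison

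*SAP*

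**What the plan says.** - **Exposure.** SAP 7.4 states that "the age of each unit of blood transfused will be calculated" and fits logistic models on "age of blood transfused (entered in different models as oldest unit transfused or as mean age of all units transfused"). It does not say what value a participant with no units takes, whether units given before randomization count, or that a unit must precede the outcome.
- **Covariates.** "The analyses will be adjusted for baseline age, RCRI, nadir Hb, and the transfusion intervention". The SAP does not say over what period nadir Hb is taken.
- **Significance level.** "0.05 for the primary outcome and 0.01 for wound infection and pneumonia". Protocol XVI.E.5 uses 0.01 for all three outcomes and also adjusts for site.
- **Output.** The first shell is "Effect of Age of Blood Transfused on Primary Outcome (ITT, mITT, No-Recent-Transfusion, Completers, Per-Protocol"). It has a Liberal vs Restrictive row with a Wald p-value and a 95% interval. Tables 25 and 26 have the same row with 99% intervals.
- **Who is transfused.** Protocol X: "Participants will be randomized to a liberal (transfuse if Hb <10 gm/dl) or restrictive (transfuse if Hb <7gm/dl) transfusion groups". Either arm may also be transfused for rapid bleeding, and the site may leave the assigned strategy after an MI.
- **Precedent.** In the preliminary study at Protocol II(a), the analysis was "adjusted for units of PRBCs transfused prior to the occurrence of any of the events" that made up its composite.

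**The concern.** There are two separate faults.

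**Selection.** Every liberal participant is below the liberal trigger at randomization, so nearly all of that arm has a blood age. In the restrictive arm, a unit after randomization needs Hb below 7, rapid bleeding, or a departure from the strategy after an MI. A fit that silently drops untransfused participants compares nearly all of one arm with a selected part of the other.

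**Reverse causation.** A unit given because an outcome has already occurred counts as exposure. In the restrictive arm it can also bring into the model a participant who would otherwise be left out, and only participants with events enter this way. The plan expects such units, because SAP Table 8 has a row for participants transfused at the attending's decision after an MI stopped the protocol. MI is a component of the primary endpoint.

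The report could then carry, under a primary-endpoint title and an ITT label, an arm odds ratio that disagrees with the randomized comparison. It could also show an association with the oldest unit that only reflects how many units were given.

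**Working it through.** **1. Yardstick from the plan.** The documents give no figure for the age-of-blood models. The design figure reproduces, using pooled variance and no continuity correction for 30% vs 22.5%: n per arm = [1.960 × √(2 × 0.2625 × 0.7375) + 1.282 × √(0.21 + 0.174375)]² / 0.075², which rounds up to 722. The total is 1444, and 1444 / 0.95 = 1520. As an odds ratio the design effect is (0.225/0.775) / (0.30/0.70) = 0.68.

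**2. Hand formula for the arm odds ratio when the truth is 1.** Suppose all liberal participants stay in the model. Let q be the share of the restrictive arm with a unit for reasons other than an outcome event. Let p be the share of otherwise untransfused restrictive participants with an event who receive a unit after it. Restrictive participants without an event stay with probability q, and those with an event with probability q + (1 − q)p. The arm odds ratio becomes q / [q + (1 − q)p].

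**3. Simulation.** There were 400,000 participants per scenario, with no arm effect and no blood-age effect. The model was logistic on arm, oldest unit and nadir Hb among participants with at least one unit.
- From the documents: a 30% event rate, the unit scheme in Protocol X, and the nadir Hb odds ratio of 0.566 from Protocol II(c), taken as per 1 gm/dl (unit assumed).
- Assumed: nadir Hb normal with mean 8.2 and SD 1, fixed before treatment; 5% given two units for bleeding; unit age uniform from 5 to 42 days; 1 + Poisson(0.5) units when a post-event transfusion occurs.

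| Units counted | q | p | Formula | Simulated arm OR | Oldest unit, OR per 10 days |
|---|---|---|---|---|---|
| Post-randomization only | 0.16 | 10% | 0.16/0.244 = 0.66 | 0.61 | 1.08 |
| | | 20% | 0.16/0.328 = 0.49 | 0.43 | 1.14 |
| | | 40% | 0.16/0.496 = 0.32 | 0.26 | 1.27 |
| Plus pre-/intraoperative units in 30% (assumed) | 0.41 | 10% | 0.41/0.469 = 0.87 | 0.89 | 1.04 |
| | | 20% | 0.41/0.528 = 0.78 | 0.77 | 1.08 |
| | | 40% | 0.41/0.646 = 0.63 | 0.63 | 1.14 |
| Plus pre-/intraoperative units in 50% (assumed) | 0.58 | 10% | 0.58/0.622 = 0.93 | 0.93 | 1.04 |
| | | 20% | 0.58/0.664 = 0.87 | 0.87 | 1.07 |
| | | 40% | 0.58/0.748 = 0.78 | 0.75 | 1.15 |

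The formula ignores the variation of q with nadir Hb, so it only approximates the fitted model.

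**4. Why the oldest unit is affected and the mean is not.** The oldest unit is a maximum. With ages uniform from 5 to 42 days its expected value for k units is 5 + 37k/(k + 1): 23.5 days for one unit, 29.7 for two, 32.8 for three. Extra units after an event raise it even when blood age does nothing. The expected mean age stays at 23.5 days, and its simulated coefficient stayed near 1.00. The arm odds ratio in the mean-age model was still biased.

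**5. Counting only pre-event units (post-randomization units only).**
- Hb alone drives transfusion, and nadir Hb is fixed before treatment: arm odds ratio 0.97 to 1.00, oldest unit 0.99 to 1.00 per 10 days.
- Bleeding also triples the odds of the outcome and is not in the model (assumed): arm odds ratio about 0.68.
- Nadir Hb is itself altered by treatment: arm odds ratio 1.4 to 1.5. This bias opposes that from post-event units; a rerun with both features and p = 10% fell back below 1.

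**The case against.** The SAP nowhere says that the models are restricted to transfused participants. This is inferred from an exposure that is undefined without a unit. The inference is sound, because no value for zero units is given, but the textual fault is an unstated analysis set.

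The restrictive group may be broader than the trigger suggests. Protocol VII.A admits patients regardless of earlier transfusion, and Protocol X records pre- and intraoperative units. This stands, and gives the milder rows above. It does not help the No-Recent-Transfusion tables: SAP 5.4 removes anyone transfused from 30 days before the operation up to randomization, so only later units remain.

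Arm is an adjustment covariate here, and the strategy effect is tested elsewhere. That is fair, and is why a footnote could replace deletion of the row.

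A reader might infer that the arm odds ratio will certainly be badly wrong and strongly favour the liberal arm. Values of 0.12 to 0.16 do arise if each event brings a mean of 1.0 to 1.5 extra units, but the documents do not support that rate:
- In Protocol Table 2 (nadir Hb 6-9), 29.5 − (11.0 + 11.1 + 0.4) = 7.0 points, or 7.0/29.5 = 24% of composite events, are at least the share that is death alone. No unit can follow these.
- The outcome runs to 90 days, but protocol transfusion ends at discharge or day 30, and the transfusion form in SAP Appendix 2 appears to stop at discharge.
- Renal failure and stroke do not by themselves release the restrictive trigger.

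The direction is not fixed either, as step 5 of the working shows.

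**Conclusion.** The concern holds in this form. The models can in practice use only participants with at least one unit. They set no limit that keeps post-outcome units out of the exposure, and they print an arm odds ratio that is not a randomized comparison and may be materially biased.

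If only post-randomization units count, a 10% post-event share is enough to move a null arm odds ratio to about 0.61, further from 1 than the 0.68 the trial is powered to detect. Every simulated size depends on inputs missing from the documents: the post-event transfusion rate, whether earlier units count, unmeasured reasons for transfusion, and the timing of nadir Hb. The oldest-unit coefficient is biased upwards by post-event units; the mean-age coefficient is little affected.

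A reader should not infer that the trial's main result is at risk. The primary Pearson test in SAP 7.1 uses all randomized participants in the ITT set and none of these models. This is an exploratory analysis whose exposure rule and table shells should be corrected before the SAP is final.

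**What to change.** In SAP 7.4 and Tables 24-26:
1. State that the analysis set is participants with at least one unit, within each named population, and say whether units given before randomization count.
2. Count only units given before the first event of the outcome being modelled. Preferably use a landmark or a time-dependent exposure; otherwise participants with an event have a shorter window to accumulate units than those without. Adjust for the number of units.
3. Define nadir Hb for these models as the lowest value before randomization.
4. Remove the Liberal vs Restrictive row, or footnote it as not an estimate of the strategy effect.
5. At the same time, reconcile the significance level and the site adjustment with Protocol XVI.E.5, or record the departure.

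The cost is SAP wording and table shells. Transfusion records are kept by study day (SAP Appendix 2), and the Cox models in SAP 7.4 already need event dates. The downside is somewhat fewer participants or units in an exploratory analysis.
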